6.3 Handling of Study Drug

Study drug will be stored at 2 - 8°C in a secure area according to local regulations. Refrigerators are required to have temperature monitoring and study staffs are required to maintain temperature monitoring logs.

6.4 Dispensing of Study Drug

It is the responsibility of the Investigators that study drug is dispensed only to study participants. Authorized personnel are the only ones to dispense product according to local regulation.

Study drug will be drawn up into syringes for ID injection. The syringes should be directly labelled with the participant identification number and date and time filled, and the syringes or cartridge put into a labelled envelope. Study drug should be administered within 6 hours from when study drug has been removed from the vial. The syringes are not to be labelled as to study drug.

6.5 Precautions with Investigational Medicinal Product

Investigational agent is to be administered only to participants who have completed informed consent for this clinical study.

6.6 Preparation of Investigational Product

Non-Luer lock TB tuberculin syringes will be loaded with 0.1 mL of GLS-5310 vaccine. For participants who are to receive vaccine at a 0.6 mg dose, a single tuberculin syringe will be filled with 0.1 mL of vaccine. For participants who are to receive vaccine at 1.2 mg dose, two tuberculin syringes will be filled to 0.1 mL. The syringes should be labelled with the participant ID#, date, and time filled.

6.7 Record of Investigational Product Disposition at Site

Investigators should maintain and manage the latest records of storage, distribution/return/disposal of investigational drugs at each site. Records and logs must comply with applicable regulations and guidelines and include the following:

- Quantity in storage at the designated place after receipt
- Quantity currently stored in the designated location
- Label identification number or batch number and expiration date
- Initials and dates of the person in charge of inventory/delivery of each investigational drug
- Quantity issued to each subject, including a unique subject identification number.
- Quantity transferred to another location/site for delivery or storage
- If applicable, the quantity discarded by the laboratory.

6.8 Return and Destruction of Investigational Product

Once monitoring of Investigational Products is completed by GeneOne or its designee, pharmacy will destroy any remaining investigational product. Pharmacy will document destruction of used and/or unused vials on the pharmacy logs.

6.9 Use of JM-11

JM-11 is a cosmetology device or an equivalent or higher device to apply mild suction.

There is no need to receive specialized training because JM-11 is brought into contact with the bleb formed after intradermal administration of GLS-5310. The operation of the device is in accordance with Section 5.2.

6.9.1 Purpose of use and principle of operation

When GLS-5310 is administered intradermally and aspirated by touching the disposable sterile tip of JM-11 to the blister formed after intradermal administration, physical stimulation is delivered

to the intradermal cells of the injection site, thereby enhancing the vaccine immune response. The physical stimulation caused by this suction is composed of a slight shear force and a compressive force that adsorbs the skin, so there is no safety concern such as skin damage.

6.9.2 Information of JM-11

-

-Product # : JM-11

-Manufacturer : Qubist

-Suction pressure and operation time : 65kPa, 30 sec

-Device

- Disposable sterile suction tip

6.9.3 Education and qualification

Intradermal administration and suction procedures do not require qualifications, but the sponsor conducts training to the investigators in advance.

6.10 Device Accountability

Sites will document the number of each type of device received and lot number. Each participant will be assigned a JM-11 device, such that devices are not to be used on multiple participants. After the 1st vaccination, the sponge protector is removed and the sponge replaced, the tip is removed and discarded, the device cleaned with an alcohol wipe, and the device placed into a plastic bag and labelled with the name of the participant. The same device is to be used for the 2nd vaccination with a new tip applied, after which processing is the same. GeneOne will instruct the site in the disposition of the devices after the study.

7. STUDY PROCEDURES AND TREATMENTS

7.1 Procedures by Visit (also see Tables S2 and S3)

7.1.1 Visit 1: Determine eligibility, obtain informed consent, enrollment, 1st vaccination

Prospective study participants will be assigned a unique participant identification number (PID#), and then interviewed to determine study eligibility.

Those who meet study criteria will complete an informed consent and be enrolled into the study to complete the following procedures:

- Review and record medical history (last 24 weeks)
- Review and record participant demographics
- Review and record prior and concomitant medications in past 24 weeks
- Perform and record physical examination and vital signs
- Record height and weight
- Collect blood for hematology and chemistry safety labs (baseline values)
- Collect blood for serological testing (Hepatitis B, Hepatitis A, HIV, Hepatitis C)
- Chest X-ray test
- 12-Lead ECG test
- PCR or Antibody screening test (SARS-CoV-2)
- Record most recent HgbA1c (diabetics only)
- Collect blood for immunology testing (serum and PBMCs baseline values)
- Collect urine for pregnancy testing (women of childbearing potential)
- Administer study drug (GLS-5310 or placebo depending on randomization results)
- Perform VAS score and record
- Distribution of subject diary after vaccination
- Check whether or not immediate adverse events (anaphylaxis-related) occur within 30 minutes after vaccination of the investigational drug (in case of the elderly over 75 years of age in Phase 2a, immediate adverse events are observed until at least 2 hours after vaccination of the investigational drug)

7.1.2 Visit 2: Safety follow-up.

Study procedures to be completed include:

- Review and record concomitant medications
- Perform targeted physical exam (relevant to participant system-specific complaints)
- Perform and record vital signs
- Review and record adverse events

- Review and record injection site reactions
- Review of subject diary
- Collect blood for hematology and chemistry

7.1.3 Visit 3: Follow-up and booster vaccination

Study procedures to be completed include:

- Review and record concomitant medications
- Perform targeted physical exam (relevant to participant system-specific complaints)
- Perform and record vital signs
- Review and record adverse events
- Collect blood for hematology and chemistry
- Collect blood for immunology testing (serum and PBMCs)
- Collect urine for pregnancy testing (women of childbearing potential)
- Administer study drug (GLS-5310 or placebo depending on randomization results)
- Perform VAS score and record
- Distribution of subject diary after vaccination
- Check whether or not immediate adverse events (anaphylaxis-related) occur within 30 minutes after vaccination of the investigational drug (in case of the elderly over 75 years of age in Phase 2a, immediate adverse events are observed until at least 2 hours after vaccination of the investigational drug)

7.1.4 Telephone Visit 1: Safety follow-up.

Study procedures to be completed include:

- Review and record adverse events
- Review and record injection site reactions

7.1.5 Visit 4: Post-vaccination follow-up, unblinding

Study procedures to be completed include:

- Review and record concomitant medications
- Perform targeted physical exam (relevant to participant system-specific complaints)
- Perform and record vital signs
- Review and record adverse events
- Review and record injection site reactions
- Collect blood for hematology and chemistry
- Collect blood for immunology testing (serum and PBMCs)
- Inform participant of their treatment assignment
 - For those who received placebo, ask whether they would like to start vaccination series with GLS-5310(Refer to Section 7.2)

7.1.6 Visits 5, 6, 7: Follow-up

Study procedures to be completed include:

- Review and record concomitant medications
- Perform targeted physical exam (relevant to participant system-specific complaints)
- Record vital signs
- Review and record adverse events
- Collect blood for immunology testing (serum and PBMCs)

7.1.10 Visit 8: End of Study or Early Termination (see above for Phase I)

Study procedures to be completed include:

- Review and record concomitant medications
- Perform targeted physical exam (relevant to participant system-specific complaints)
- Record vital signs
- Review and record adverse events
- Collect blood for hematology and chemistry
- Collect blood for immunology testing (serum and PBMCs)

7.1.11 Unscheduled visits

Study procedures to be completed include:

- Review and record concomitant medications
- Perform targeted physical exam (relevant to participant system-specific complaints)
- Perform and record vital signs
- Review and record adverse events

7.2 Procedures by Visit (GLS-5310 revaccination group, see clinical trial schedule S4)**7.2.1 Visit 1: Vaccination**

- Review and record prior and concomitant medications
- Perform and record physical examination and vital signs
- Collect blood for hematology and chemistry safety labs (baseline values)
- Collect blood for immunology testing (serum and PBMCs baseline values)
- Collect urine for pregnancy testing (women of childbearing potential)
- Administer study drug (GLS-5310)
- Perform VAS score and record
- Distribution of subject diary after vaccination
- Check whether or not immediate adverse events (anaphylaxis-related) occur within 30 minutes after vaccination of the investigational drug (in case of the elderly over 75 years of age in Phase 2a, immediate adverse events are observed until at least 2 hours after vaccination of the investigational drug)

7.2.2 Visit 2: Safety follow-up.

Study procedures to be completed include:

- Review and record concomitant medications
- Perform targeted physical exam (relevant to participant system-specific complaints)
- Perform and record vital signs
- Review and record adverse events
- Review and record injection site reactions
- Review of subject diary
- Collect blood for hematology and chemistry

7.2.3 Visit 3: Follow-up and booster vaccination

Study procedures to be completed include:

- Review and record concomitant medications
- Perform targeted physical exam (relevant to participant system-specific complaints)
- Perform and record vital signs
- Review and record adverse events
- Collect blood for hematology and chemistry
- Collect blood for immunology testing (serum and PBMCs)
- Collect urine for pregnancy testing (women of childbearing potential)
- Administer study drug (GLS-5310)
- Perform VAS score and record
- Distribution of subject diary after vaccination
- Check whether or not immediate adverse events (anaphylaxis-related) occur within 30 minutes after vaccination of the investigational drug (in case of the elderly over 75 years of age in Phase 2a, immediate adverse events are observed until at least 2 hours after vaccination of the investigational drug)

7.2.4 Telephone Visit 1: Safety follow-up.

Study procedures to be completed include:

- Review and record adverse events
- Review and record injection site reactions

7.2.5 Visit 4: Post-vaccination follow-up

Study procedures to be completed include:

- Review and record concomitant medications
- Perform targeted physical exam (relevant to participant system-specific complaints)
- Perform and record vital signs
- Review and record adverse events
- Review and record injection site reactions
- Collect blood for hematology and chemistry
- Collect blood for immunology testing (serum and PBMCs)
- Inform participant of their treatment assignment

7.2.6 Visits 5, 6, 7: Follow-up

Study procedures to be completed include:

- Review and record concomitant medications
- Perform targeted physical exam (relevant to participant system-specific complaints)
- Record vital signs
- Review and record adverse events
- Collect blood for immunology testing (serum and PBMCs)

7.2.10 Visit 8: End of Study or Early Termination

Study procedures to be completed include:

- Review and record concomitant medications

- Perform targeted physical exam (relevant to participant system-specific complaints)
- Record vital signs
- Review and record adverse events
- Collect blood for hematology and chemistry
- Collect blood for immunology testing (serum and PBMCs)

7.2.11 Unscheduled visits

Study procedures to be completed include:

- Review and record concomitant medications
- Perform targeted physical exam (relevant to participant system-specific complaints)
- Perform and record vital signs
- Review and record adverse events

7.3 Timing and Evaluations

7.3.1 Informed Consent

Study personnel will meet with prospective study participants, explain the study, and provide them with an informed consent form (ICF) that describes the screening tests, eligibility criteria for entering the study, study treatments and follow-up procedures. An informed consent must be signed prior to any study related procedures being performed. A copy of the signed and dated consent form will be given to the participant.

7.3.2 Enrollment and Intake visit

Participants who consent to be in the study will be assigned a unique PID#. Once assigned, PID#s cannot be reused for any reason. Information regarding participant's PID# and screen date will also be documented on a screening log.

Medical History

Investigators should document all significant illnesses that the participant has experienced as Medical History within the past 24 weeks. Illnesses' first occurring or detected during the study and/or worsening of an existing illness that occurs after the first administration of study drug are documented as AEs on the electronic case report form (eCRF).

Prior / Concomitant medications

Prior treatments for a period of 24 weeks prior to enrollment will be recorded. Concomitant treatments, defined as continuing or new treatments taken at or after the signing of the informed consent, will be recorded in the eCRF as concomitant medications.

7.3.3 Adverse effects

Adverse effects that will be queried at each study visit include those related to the underlying disease and treatment, those potentially related to study drug, and those potentially related to study drug administration. AEs should be graded according to the "Toxicity Grading Scale for Healthy Adult and Adolescent Volunteers Enrolled in Preventative Vaccine Clinical Trials" issued in September 2007 by the US FDA (Appendix A). Subjects record the response (local and systemic) after vaccination on the evening of each vaccination day and 7 days after each vaccination day in the subject diary (Appendix B).

Subjects record the response to the injection site using the measurement tool provided, and the investigator reviews the subject diary. The response results described are evaluated for clinical significance and recorded as appropriate in the CRF.

Subjects who develop Grade 1 or higher eosinophilia (eosinophil count of ≥ 650 cells/mm³) will be asked to return weekly for repeat CBC determinations until resolution of the eosinophilia.

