7.4 Assessment of injection site

The injection site will be assessed by study personnel at each visit. Participants are to be instructed to monitor the site for signs of inflammation, redness, swelling, or pain and report these issues at the next study visit. Site staff will discuss any symptoms and determine whether these constitute AEs and record as appropriate. The subject should be instructed to record the exact symptoms, the diameter of the redness (cm), the diameter of the edema (cm), the diameter of the bruise (cm), and the date of onset and disappearance.

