8.1.2.1.3 Solicited local/systemic AE

In the vaccination of this investigational drug, a feeling of pulling the skin may occur due to suction, and potential adverse events of the investigational drug may include erythema, pain, heat, or partial swelling at the injection site. Other adverse events that occur are included in the unexpected adverse events.

The solicited local and systemic adverse events can be summarized as follows.

Table 8.1.2.1.3-1 Solicited local/systemic AE

Common	
 Mild to moderate administration site pain, erythema, tenderness, swelling, induration Malaise/fatigue, myalgia, or headache in the first few days following injection Visible lesion(s) at the injection site, such as erythematous papules with eschar, hypopigmentation, hyperpigmentation
Less common	
 Administration site bruising/ecchymosis, hematoma or pruritus Arthralgia or nausea Injection site hematoma, bruising/ecchymosis, laceration, other transient lesions, or bleeding related to the injection procedure Eosinophilia
Uncommon or rare	
 Administration site, laceration, other transient lesions, or bleeding related to the injection procedure Severe administration site pain or tenderness Rash following injection/EP Keloid scar or hypertrophic scar formation Transient changes in clinical laboratory values
Unknown frequency or theoretical potential risks	
 Severe localized administration site reaction, such as sterile abscess or secondary bacterial infection Allergic reaction, including urticaria, angioedema, bronchospasm, or anaphylaxis Chills, flu-like syndrome Muscle damage at the administration site Autoimmune disease Effects on the fetus and on pregnancy

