8.2 Methods and Timing for Collection and Recording of Safety Data

At the time of each study visit, participants will be queried as to adverse events that have occurred in the interim period and the current status of any AE that was reported at a prior visit that has not yet resolved. Additionally, labs will be reviewed for safety.

All AEs, regardless of severity, seriousness, or presumed relationship to study treatment, must be recorded using medical terminology in source documents and on the eCRF. Whenever possible, a diagnosis will be documented, in lieu of symptoms. The source document and the eCRF must contain the Investigator's opinion concerning the relationship of the AE to study treatment.

AEs should be described with the following attributes:

- Duration (start and end dates)
- Seriousness
- Severity
- Causality
- Action(s) taken
- Outcome

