12.6.1 Study Reporting Period of Adverse Events

All solicited and unsolicited adverse events are collected during the entire study period and recorded in the eCRF.

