2.1 Safety Endpoints

- Adverse Events (AEs)
- Vital signs
- Laboratory tests
- Assessment of Injection Site - The Solicited local AEs and Solicited Systemic AEs

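### Protocol 7.3.3 and 7.4 let sites judge participant-recorded reactions before CRF entry, in conflict with 8.2 and 12.6.1, so mild reactions may be under-counted and recorded unevenly across sites

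*Protocol*

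**What the plan says.** **Collection.** Protocol 7.3.3: "Subjects record the response (local and systemic) after vaccination on the evening of each vaccination day and 7 days after each vaccination day", in a diary. Section 7.4 adds that participants note symptoms, dates of onset and disappearance, and the diameters of redness, edema and bruising.

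**Step before the CRF.** Section 7.3.3, on the diary responses: "The response results described are evaluated for clinical significance and recorded as appropriate in the CRF". Section 7.4, on injection-site symptoms: "Site staff will discuss any symptoms and determine whether these constitute AEs and record as appropriate".

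**Recording rules elsewhere.** Section 8.2: "All AEs, regardless of severity, seriousness, or presumed relationship to study treatment, must be recorded using medical terminology in source documents and on the eCRF". Section 12.6.1: "All solicited and unsolicited adverse events are collected during the entire study period and recorded in the eCRF".

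**What counts as an adverse event.** The definition within section 8.1.2.1 covers any unwanted sign or symptom and sets no significance threshold. Table 8.1.2.1.3-1 lists among the common solicited events: "Mild to moderate administration site pain, erythema, tenderness, swelling, induration". Section 8.1.2.1.6 provides a mild grade.

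**Analysis.** SAP 2.1 names as a safety endpoint: "Assessment of Injection Site - The Solicited local AEs and Solicited Systemic AEs". SAP 10.2.1 and 10.2.2 then summarise solicited local and systemic events as TEAEs, ADRs, SAEs and SADRs. The severity tables listed in 10.2.2 are for TEAEs and ADRs overall, not for solicited events.

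**The concern.** Adverse events graded on the vaccine toxicity scale are a primary endpoint in both phases. In a small vaccine study much of that endpoint is reactogenicity, and a diary exists so that it can be measured the same way in everyone. If sites first ask whether an entry is clinically significant, or whether it amounts to an adverse event, mild reactions are the ones most likely to be left out. The reported rate would then depend partly on each site's threshold.

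The judgement would be made at 5 sites. It is unblinded in open-label Phase I, where staff know the dose, and in placebo participants who take GLS-5310 after Visit 4, whose safety is reported separately. The SAP text offers no second route by which an omitted diary entry would be seen.

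**Working it through.** The plan states no figure on this point, so the check is mainly a comparison of texts.

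**1. Does 7.3.3 decide whether an entry is recorded, or only how?** Its wording allows both readings. Elsewhere the protocol uses clinical significance to decide whether. Section 8.1.2.1.5 records laboratory, vital-sign and ECG abnormalities when they are significant, section 8.1.5 reports a laboratory value as an event only if significant, and the exclusions under the adverse event definition remove non-significant laboratory findings. A site could reasonably read 7.3.3 the same way, and 7.4 expressly asks whether a symptom is an event.

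**2. Do 8.2 and 12.6.1 settle it?** Both govern things already classed as adverse events. Section 7.4 gives that classification to site staff, so a symptom judged not to be an event falls outside both rules. Under the protocol's own definition and Table 8.1.2.1.3-1, however, a mild site reaction is an event. The sections therefore conflict, and sites may resolve the conflict differently.

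**3. Can staff examination replace the diary?** Not fully. In Table S2 the second dose is at Week 8, the next contact is by telephone at Week 9, and the next in-person examination is at Week 12, nominally 28 days after the dose (day 84 minus day 56 in SAP Table 2). In Table S3 the sequence is Weeks 12, 13 and 16, the same gap. Measured reactions in the 7 days after the second dose thus rest largely on what the participant recorded.

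**4. Does the SAP recover omitted entries?** Its text describes no summary of diary entries or diameters.

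**5. Size.** Let p_v and p_p be the true proportions with a reaction (vaccine, placebo), and c_v and c_p the shares of those that are recorded.

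Recorded difference = c_v × p_v − c_p × p_p

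None of the four quantities is in the documents. For illustration only, assume p_v = 64% and p_p = 36%, a gap of 28 points. The synopsis cites that gap for 126 participants; the base rate is my assumption.

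| c_v | c_p | Recorded rates | Difference (points) |
|---|---|---|---|
| 1.0 | 1.0 | 64 v 36 | 28 |
| 0.9 | 0.9 | 57.6 v 32.4 | 25.2 |
| 0.75 | 0.75 | 48 v 27 | 21 |
| 0.5 | 0.5 | 32 v 18 | 14 |
| 0.9 | 0.5 | 57.6 v 18 | 39.6 |
| 0.5 | 0.9 | 32 v 32.4 | −0.4 |

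Omission can only lower each arm's rate. Equal omission shrinks the difference in proportion. If mild reactions are dropped most and severity differs between arms, the shares differ too, and the difference can move either way even when the judgement is blinded. Neither its size nor its direction can be fixed from the documents.

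**The case against.** The strongest reply is that the protocol already requires full recording. Section 12.6.1 is the most direct statement on solicited events and it is unqualified; 8.2 covers all severities; 3.1 and 8.3 say that reactions and complaints are documented. The definition, the solicited-event table and the mild grade all mean that staff applying 7.4 correctly should count a mild site reaction. The stated exclusion of non-significant findings concerns laboratory values only. The schedules and most of the relevant visit lists also have an injection-site recording step separate from adverse event recording, with no filter attached.

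Much of this stands. A reader might infer that reactions reach the CRF only once judged significant, and that the endpoint is in fact under-counted. The documents do not support that: 8.2 and 12.6.1 say otherwise, and the wording of 7.3.3 can be read as governing how an entry is recorded. A reader might also infer that site reactions are the commonest known harm of this vaccine. Table 8.1.2.1.3-1 lists them as common but gives no ranking or rates, and section 1.4 calls the adverse effects of GLS-5310 unknown.

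The diary form (Appendix B), the CRF and the SAP table shells are not in the text available, and might show item-by-item transcription. The statement about the SAP therefore applies to its body text only.

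What the reply does not remove is the instruction in 7.3.3 and 7.4. The separate injection-site step does not name the CRF as its destination, and the requirement to document a reaction is not a requirement to enter it.

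**Conclusion.** The concern holds as a conflict between sections that creates a risk of under-recording. Sections 7.3.3 and 7.4, followed as written, could drop mild reactions that 8.2, 12.6.1 and the protocol's own definitions would keep, and the SAP text would not recover them. The result may be reaction rates that are too low and that vary by site.

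No percentage bias can be attached to this; the table above only shows how the result would depend on assumed values. A reader might infer that the vaccine-placebo difference must be understated, but that follows only if the same share is omitted in both arms. Phase IIa judgement is blinded up to Visit 4, which limits deliberate differences between arms but does not make the shares equal. Because SAP section 5 describes a descriptive trial without hypothesis tests, the consequence is a biased estimate and confidence interval rather than lost power. The Grade 3 criterion for entering Phase IIa is unlikely to be affected, since the doubt concerns mild reactions.

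**What to change.** Reconcile protocol 7.3.3 and 7.4 with 8.2 and 12.6.1. State that each solicited symptom and each measurement in the diary is entered in the eCRF as the participant reported it and graded on the protocol's Toxicity Grading Scale, with no clinical-significance filter. Keep investigator judgement for causality and seriousness.

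In SAP 10.2.2, build the solicited local and systemic tables from these entries, by maximum grade per participant. If the diary form, CRF or table shells already provide for this, cite them in both documents.

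The cost is revised protocol and CRF-guideline wording, more diary data entry, and a changed source for the solicited tables. The reported rate of mild reactions may rise. No visit or procedure is added. Section 12.2 gives participant diaries as an example of source documents, so entries from diaries already collected could be transcribed retrospectively.
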